### 6.3.2 Decimal Places

Listings, minimum and maximum will contain the number of decimal places that is clinically meaningful specific to each parameter. Means, medians and percentiles will be displayed to 1 more decimal place than min and max. Dispersion statistics (eg standard deviation) will have 2 more decimal places than min and max. Percentages will be displayed with 1 decimal place.

For PK data, individual concentrations and PK parameters will be reported to 3 significant figures. For summary statistics, n will be reported as a whole number; mean, SD, median, min, max, geometric mean, CV%, and geometric mean CV% will be reported to the same precision as for individual data.

### 6.4 Participant Disposition

Participant disposition will be summarized as follows:

- The number of participants who are in each analysis population will be summarized overall for Screened Participants.
- The number of early withdrawals and the reasons for withdrawals will be tabulated by dose and overall for the ITT Population.
- The number of screened participants, rescreened participants, and screen failures and the reasons for screen failure will be tabulated overall for the Screened Participants population.

### 6.5 Protocol Deviations

A listing of protocol deviations will be provided within Appendix 16.2 of the CSR.

### 6.6 Baseline Comparability

The comparability of doses with respect to participant demographics and baseline characteristics will be assessed in a descriptive manner, but no formal statistical testing will be performed.

Standard continuous or categorical variable summaries will be presented overall for the following variables based on the Safety Population:

- Age at Informed Consent (years),
- Sex (Male, Female),
- Fertility Status (Childbearing Potential, Post-menopausal, Surgically Sterile)
- Ethnicity (Hispanic or Latino, Not Hispanic or Latino),

|   |  |                                  |  |
|---|--|----------------------------------|--|
|   |  | Confidentiality Statement |  |
| This document is the property of [REDACTED] and may not be duplicated, copied, altered or removed from company without prior approval from [REDACTED] or in compliance with [REDACTED]. |  |                                  |  |

|  |  |                  |                         |
|--|--|------------------|-------------------------|
|  |  | Sponsor:         | Pliant Therapeutics Inc |
|  |  | Protocol Number: | PLN-74809-IPF-201       |
| STATISTICAL ANALYSIS PLAN – PHASE 1 |  |                  |                         |

- Race (American Indian or Alaska Native, Asian, Black or African American, Native Hawaiian or Other Pacific Islander, White, Multiple Race),
- Height at Screening (cm),
- Weight at Screening (kg),
- BMI at Screening (kg/m^2)
- Pulmonary Function at Screening,
- DLCO,
- GAP Staging,
- Months since IPF diagnosis,
- Received nintedanib as standard of care prior to randomization (Yes, No),
  - If yes, duration of nintedanib use (months),
- Received pirfenidone as standard of care prior to randomization (Yes, No),
  - If yes, duration of pirfenidone use (months)

All demographic and baseline characteristic data will be listed.

## 6.7 Medical History

The number of participants with previous and ongoing conditions at screening will be summarized by system organ class and preferred term for the Safety Population. Previous and ongoing conditions at screening will be listed for the Safety Population. Conditions will be presented by Medical Dictionary of Regulated Activities (MedDRA) (version 4.0) system organ class and preferred term.

## 6.8 Prior and Concomitant Medications and Non-Pharmacological Procedures

The number of prior and concomitant medications will be summarized by Anatomical Therapeutic Chemical (ATC) Classification level 4 term and preferred term for the Safety Population. Prior and concomitant medications will be summarized separately. Prior and concomitant medications and non-pharmacological procedures will be listed for the Safety Population. Medications will be coded using the World Health Organization Drug Dictionary (WHODD) [REDACTED] ATC Classification System level 4 term and preferred term.

Prior medications are defined as all medications starting and stopping before the date of first dose of study drug. Concomitant medications are defined as medications taken on or after the date of first dose of study drug.

|  |  |                                  |  |
|--|--|----------------------------------|--|
|  |  | Confidentiality Statement |  |
| This document is the property of [REDACTED] and may not be duplicated, copied, altered or removed from company without prior approval from [REDACTED] or in compliance with [REDACTED] |  |                                  |  |

|  |  |                  |                         |
|--|--|------------------|-------------------------|
|  |  | Sponsor:         | Pliant Therapeutics Inc |
|  |  | Protocol Number: | PLN-74809-IPF-201       |
| STATISTICAL ANALYSIS PLAN – PHASE 1 |  |                  |                         |

Use and duration of Pirfenidone and Nintedanib will be summarized overall using standard continuous or categorical variable summaries.

## 6.9 Exposure to Study Drug

The number of participants who have received each dose, and the order received, will be summarized by dose and overall, for the Safety Population.

All dosing information will be listed.

## 6.10 Statistical Analysis of Pharmacokinetic Data

### 6.10.1.1 Concentration-time Data

Plasma samples for PK analysis will be obtained predose and at 0.5, 1, 2, 3, and 4 hours after dosing on Day 1 (prior to receiving the R01 Knottin tracer) and at 24 hours after dosing (Day 2). A collection window of  $\pm 5$  minutes will be allowed for samples up to 1-hour post-dose and a collection window of  $\pm 10$  minutes will be allowed for samples that are collected at 2 hours post-dose and after. Concentrations collected significantly outside of the collection windows will be discussed with the Sponsor prior to summarizing concentration-time data.

The percent (%) unbound PLN-74809 will also be determined at 0.5, 1, 2, 3, and 4, and 24 hours after dosing on Day 1. Unbound plasma PLN-74809 concentrations will be calculated as percent unbound x total plasma concentration at each time point.

Plasma PLN-74809 concentrations (total and unbound) at each sampling time point will be presented in listings and summarized by dose with descriptive statistics. Mean plasma (total and unbound) PLN-74809 concentration-versus-time profiles (with plasma concentrations on both a log and linear scale) will be plotted for each dose. Concentration-versus-time plots will also be provided for each participant. For presentation of the individual data and summary statistics, concentrations below the limit of quantitation (BLQ) will be set to zero. Percent unbound at each time point will be presented in listings and summarized by dose with descriptive statistics. BLQ values will be presented as BLQ (<1.00 ng/mL) in the concentration listing (ie, these will not be set to zero).

### 6.10.1.2 PK Parameters

Concentration-time data for PLN-74809 will be analyzed using noncompartmental methods in Phoenix® WinNonlin® [REDACTED] in conjunction with the internet-

|  |  |                                  |  |
|--|--|----------------------------------|--|
|  |  | Confidentiality Statement |  |
| This document is the property of [REDACTED] and may not be duplicated, copied, altered or removed from company without prior approval from [REDACTED] or in compliance with [REDACTED] |  |                                  |  |

|  |  |                  |                         |
|--|--|------------------|-------------------------|
|  |  | Sponsor:         | Pliant Therapeutics Inc |
|  |  | Protocol Number: | PLN-74809-IPF-201       |
| STATISTICAL ANALYSIS PLAN – PHASE 1 |  |                  |                         |

accessible implementation of Pharsight® Knowledgebase Server™ [REDACTED]  
[REDACTED]

During the PK analysis, BLQ concentrations up to the time of the first quantifiable concentration will be treated as zero. Embedded (values between 2 quantifiable concentrations) and terminal BLQ concentrations will be treated as “missing”. PK analysis will be performed using actual time relative to dosing. Descriptive statistics will be used to summarize the PK parameters by dose. Individual PK parameters will be provided in listings. Subjects will be referred to as “participant”.

The following PK parameters will be calculated for PLN-74809 in plasma:

| Parameter         | Definition   |
|-------------------|--|
| $C_{max}$         | Maximum observed plasma drug concentration, determined directly from individual concentration-time data  |
| $T_{max}$         | Time to maximum observed plasma concentration, determined directly from individual concentration-time data   |
| $AUC_{0-4}$       | Area under the plasma concentration-time curves from time 0 to 4 hours postdose
Calculated using Linear-Up Log-Down Method                              |
| $AUC_{0-24}^a$    | Area under the plasma concentration-time curves from time 0 to 24 hours postdose
Calculated using Linear-Up Log-Down Method                             |
| $AUC_{last}$      | Area under the plasma concentration-time curves from time 0 to the time of the last detectable concentration
Calculated using Linear-Up Log-Down Method |
| $C_{avg}^a$       | Average concentration
Calculated as $AUC_{0-24}/24$   |
| $C_{max, u}$      | Unbound $C_{max}$ , calculated using unbound plasma concentrations.  |
| $AUC_{0-4, u}$    | Unbound $AUC_{0-4}$ , calculated using unbound plasma concentrations   |
| $AUC_{0-24, u}^a$ | Unbound $AUC_{0-24}$ , calculated using unbound plasma concentrations  |
| $AUC_{last, u}$   | Unbound $AUC_{0-24}$ , calculated using unbound plasma concentrations  |
| $C_{avg, u}$      | Unbound $C_{avg}$ ,
calculated as $AUC_{0-24,u}/24$   |

a As no samples were collected between 4 and 24 hours, total and unbound  $AUC_{0-24}$ ,  $AUC_{last}$ ,  $C_{avg}$  may be overestimated.  $AUC_{0-24}$  may be overestimated by approximately 12%. This may be discussed in the CSR as warranted.

|  |  |                                  |  |
|--|--|----------------------------------|--|
|  |  | Confidentiality Statement |  |
| This document is the property of [REDACTED] and may not be duplicated, copied, altered or removed from company without prior approval from [REDACTED] or in compliance with [REDACTED] |  |                                  |  |

|  |  |                  |                         |
|--|--|------------------|-------------------------|
|  |  | Sponsor:         | Pliant Therapeutics Inc |
|  |  | Protocol Number: | PLN-74809-IPF-201       |
| STATISTICAL ANALYSIS PLAN – PHASE 1 |  |                  |                         |

The validated method used for this study:

[REDACTED]

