6.8 Pharmacokinetic Assessments

Plasma samples for PK analysis will be obtained before and at 0.5, 1, 2, 3, and 4 hours after dosing on Day 1 (prior to receiving the R_01 Knottin tracer) and at 24 hours after dosing (Day 2). A collection window of ± 5 minutes will be allowed for samples up to 1-hour post-dose and a collection window of ± 10 minutes will be allowed for samples that are collected at 2 hours post-dose and after. Samples will be obtained and stored as detailed in the study PK Manual.

The actual collection time of each sample must be recorded in the source data and on the eCRF. If the participant discontinues the study early, a plasma sample for PK should be taken at the Early Termination (ET) Visit if possible.

Aliquots of these PK samples may be used to measure nintedanib and or pirfenidone concentrations in participants receiving these drugs.

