9.4 Pharmacokinetic Analysis

Plasma PLN-74809 concentrations at each sampling time point will be presented in listings and summarized with descriptive statistics. Plasma PLN-74809-versus-time profiles (with plasma concentrations on both a log and linear scale) will be plotted for each participant.

Non-compartmental analysis will be used to calculate the PK parameters T_{max} , C_{max} , area under the drug concentration-time curve from time zero to the time of the last measurable concentration (AUC_{last}), AUC from time zero to 4 hours (AUC₍₀₋₄₎) and from time zero to 24 hours (AUC₍₀₋₂₄₎) after dosing, and average drug concentration (C_{avg}), if applicable. Plasma PK parameters will be presented in listings and summarized with descriptive

Confidential Page 316 of 331

statistics. Further details of the analyses will be provided in the SAP, which will be prepared and agreed prior to final database lock at the end of the study. The PK analysis plan and report may be prepared separately from the SAP, as appropriate.

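### The SAP defines unbound AUClast as unbound AUC0-24, duplicating the row above it and contradicting its own definition of total AUClast and the protocol's

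*SAP*

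**What the plan says.** The parameter table in SAP section 6.10.1.2 defines total AUClast as "Area under the plasma concentration-time curves from time 0 to the time of the last detectable concentration", by the linear-up log-down method. This agrees with Protocol section 9.4: "area under the drug concentration-time curve from time zero to the time of the last measurable concentration". The unbound counterpart reads "AUC_{last, u}$ | Unbound $AUC_{0-24}$ , calculated using unbound plasma concentrations", the same definition as the AUC0-24,u row directly above it. Both rows are complete, so neither a redaction nor a broken table explains the match. SAP section 9 visibly reports changes from the protocol only for the analysis populations.

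Four other provisions bear on the point:

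- **Sampling.** SAP section 6.10.1.1 schedules plasma "predose and at 0.5, 1, 2, 3, and 4 hours after dosing on Day 1" "and at 24 hours after dosing (Day 2)". Nothing is scheduled between 4 and 24 h. Percent unbound is planned at the post-dose times of this schedule only.
- **Values below the limit.** In section 6.10.1.2, "Embedded (values between 2 quantifiable concentrations) and terminal BLQ concentrations will be treated as" missing, so AUClast ends at the last quantifiable sample.
- **Summaries.** PK parameters are summarised by dose and listed individually.
- **Early termination (ET).** Protocol section 6.8 says that on early discontinuation "a plasma sample for PK should be taken at the Early Termination (ET) Visit if possible".

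**The concern.** The label and the definition of AUClast,u disagree, and this table is what the PK programmer works from. Taken literally, one planned parameter is never calculated and another appears under two names. Anyone who sets total AUClast beside unbound AUClast would assume that both cover the same interval, and the table does not ensure that.

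The sampling schedule decides when this matters. With a 20-hour gap before the last scheduled sample, losing the 24 h value moves the end of AUClast from 24 h straight to 4 h. Total AUClast would then stop at 4 h, while the row labelled AUClast,u would still call for an area to 24 h. That area could come only from extrapolation, or it would be missing. The visible text gives no rule for either.

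**Working it through.** **Step 1. The definitions side by side.**

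| Parameter | Source | End of interval |
|---|---|---|
| AUClast, total | Protocol 9.4 | last measurable concentration |
| AUClast, total | SAP 6.10.1.2 | last detectable concentration |
| AUC0-24,u | SAP 6.10.1.2 | 24 h |
| AUClast,u | SAP 6.10.1.2 | 24 h (same as AUC0-24,u) |

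The first two rows agree. The last contradicts its own label. This step needs no assumption.

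**Step 2. Size when the 24 h sample is quantifiable.** The documents give no half-life or concentrations, so a model has to be assumed:

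- C(t) = ka/(ka − ke) × [exp(−ke·t) − exp(−ka·t)], with ke = ln 2 / half-life.
- ka is solved from ln(ka/ke)/(ka − ke) = Tmax.
- Tmax is 4 h, the approximate value in Protocol section 3.1.
- Half-life is taken from 12 to 60 h (assumption).

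The SAP uses actual times and allows ±10 min at 24 h, so AUClast can end slightly before or after 24 h. On the SAP's sampling grid with linear-up log-down, AUClast/AUC0-24 is 0.9965 to 1.0035 at a half-life of 12 h and 0.9937 to 1.0063 at 60 h. Widening the assumptions to Tmax 2 to 4 h and half-life 6 to 100 h gives 0.993 to 1.007. The wording error therefore changes the number by less than about 1%.

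**Step 3. Size when the profile ends at 4 h.** Same model, ratio AUC0-4/AUC0-24:

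| Half-life (h) | 12 | 24 | 36 | 48 | 60 |
|---|---|---|---|---|---|
| Exact integral | 0.190 | 0.166 | 0.158 | 0.154 | 0.152 |
| SAP grid, linear-up log-down | 0.194 | 0.166 | 0.157 | 0.153 | 0.151 |

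A correctly defined AUClast,u for such a profile is about 0.15 to 0.19 of AUC0-24,u.

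**Step 4. What one such profile could do to a dose summary.** Assume four participants at a dose with equal exposure, and one profile truncated at ratio 0.16. The arithmetic mean AUClast becomes (3 + 0.16)/4 = 0.79 of its full value, 21% lower. The geometric mean becomes 0.16^(1/4) = 0.63, 37% lower. The group size and the missing sample are both assumptions; the documents report neither.

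**Step 5. How likely is a 24 h value below the limit?** In the same model C(24)/Cmax is 0.345 at a half-life of 12 h and 0.802 at 60 h. Against the 1.00 ng/mL limit in SAP section 6.10.1.1, the 24 h value is below it only if Cmax is under 1.00/0.345 = 2.9 ng/mL or 1.00/0.802 = 1.25 ng/mL respectively. Nothing in the documents points to concentrations that low. The realistic route to a 4 h end is a sample that was not taken or not usable.

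**The case against.** The strongest reply is that this is a copying slip in one cell, which a PK analyst would correct unprompted because the label says what is meant. Protocol section 9.4 also allows a separate PK analysis plan, which is not among the documents and may carry the right definition. AUC0-4 and AUC0-24, total and unbound, are in the same table with fixed intervals. The summaries include n, median, minimum and maximum, and individual values are listed. All of this stands and limits the harm. It does not make the row correct.

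A reader might go further and infer that the by-dose AUClast summaries are wrong or not comparable in general, because profiles can end at 4 h, at 24 h or at an ET sample. The documents do not support that:

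- An end time that varies between profiles is inherent in AUClast, and total AUClast is defined in the usual way.
- No SAP text brings the ET sample into the noncompartmental analysis. Section 6.10.1.1 lists only predose to 24 h, and the schedule of events shows no plasma PK sample at the EoT/EoS/ET visit. Percent unbound is not planned at ET, so an unbound area to that sample would not normally be computable.
- The table's footnote on the 4 to 24 h gap names AUClast together with AUC0-24, which suggests that the authors expect AUClast to reach 24 h.
- Nothing shows that any 24 h sample is missing.

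The visible SAP also plans no unbound-to-total ratio based on AUClast, so harm to such a ratio is hypothetical.

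**Conclusion.** The AUClast,u row is wrong as written. It duplicates AUC0-24,u, contradicts the SAP's own total AUClast and departs from the protocol's definition of AUClast. Followed literally, unbound AUClast is never produced.

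The numerical effect is conditional. It is under about 1% for every profile with a quantifiable 24 h sample, and material only for a profile that ends at 4 h. The ratio of 0.15 to 0.19 for such a profile rests on the assumed one-compartment shape, Tmax of 4 h and half-life of 12 to 60 h.

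The point is minor. PK is summarised descriptively, no hypothesis is tested, the primary endpoint is PET-based, and total AUClast is sound. The SAP's silence on the ET sample is a matter for clarification, not an error.

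**What to change.** Replace the AUClast,u definition in the table of SAP section 6.10.1.2 with: area under the unbound plasma concentration-time curve from time 0 to the last quantifiable unbound concentration, by linear-up log-down. This matches total AUClast and costs one table cell. If a separate PK analysis plan exists, check that it says the same.

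Two optional clarifications, a sentence each:

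- State that an ET plasma sample taken after 24 h does not enter AUClast.
- List the time of the last quantifiable sample for each profile, so that any profile ending at 4 h can be recognised behind the by-dose summary.

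I would not restrict the AUClast summary to profiles that reach 24 h. That would make it almost a copy of AUC0-24. If 24 h values were below the limit, it would also drop the lowest exposures and push the dose mean upward.

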## 6.11 Safety Analyses

The safety analyses will be presented by the dose received for the Safety Population.

### 6.11.1 Adverse Events

A TEAE is defined as:

- Any AE that has an onset on or after the first dose of study drug.
- Any pre-existing AE that has worsened in severity on or after the first dose of study drug.

AEs will be classified as either related or not related to the study drug. If an AE has missing relationship, it is assumed to be related to the study drug for analysis purposes.

AEs will also be classified as either related or not related to study procedure. If an AE has missing relationship, it is assumed to be related to study procedure for analysis purposes.

Severity of the AE will be graded using the Common Terminology Criteria for Adverse Events (CTCAE) grading system (Version 5.0): Grade 1 (Mild), Grade 2 (Moderate), Grade 3 (Severe), Grade 4 (Life-Threatening), Grade 5 (Death). Grade 3 (Severe) will be assumed for an AE with missing grade.

The following tables will be presented for AEs:

- Number (%) of participants with TEAEs, study drug-related TEAEs, procedure-related TEAEs, serious TEAEs, TEAEs leading to withdrawal, and TEAEs leading to death, by dose and overall.
- Number (%) of participants with TEAEs by system organ class and preferred term, dose and overall.
- Number of events of TEAEs by system organ class and preferred term, dose and overall.
- Number (%) of participants with study drug-related TEAEs by system organ class and preferred term, dose and overall.
- Number (%) of participants with procedure-related TEAEs by system organ class and preferred term, dose and overall.
- Number (%) of participants with TEAEs by system organ class, preferred term, maximum severity, dose and overall.

[figure not shown]
|   |  |                                  |  |
|---|--|----------------------------------|--|
|   |  | Confidentiality Statement |  |
| This document is the property of [REDACTED], and may not be duplicated, copied, altered or removed from company without prior approval from [REDACTED] or in compliance with [REDACTED] |  |                                  |  |

|  |  |                  |                         |
|--|--|------------------|-------------------------|
|  |  | Sponsor:         | Pliant Therapeutics Inc |
|  |  | Protocol Number: | PLN-74809-IPF-201       |
| STATISTICAL ANALYSIS PLAN – PHASE 1 |  |                  |                         |

- [REDACTED]
- [REDACTED]
- Listing of Serious Adverse Events (SAEs) (presented in the Table section of the appendices).
- Listing of AEs leading to withdrawal from study (presented in the Table section of the appendices).
- Listing of AEs leading to death (presented in the Table section of the appendices).

[REDACTED]

[REDACTED]

In counting the number of AEs reported, a continuous event (ie reported more than once and which did not cease), will be counted only once; non-continuous AE reported several times by the same participant will be counted as multiple events.

Where a preferred term is reported more than once, the most related or maximum severity will be counted.

When summarizing TEAEs by dose, TEAEs will be allocated to the most recent dose received prior to onset of the TEAE. TEAEs that increase in severity will be counted as a separate TEAE and allocated to the most recent dose received prior to the increase in severity.

All AEs will be listed.

